7. DEFINITIONS OF POPULATIONS

Any protocol deviations, including those related to COVID-19, will be considered prior to database lock for their importance and taken into consideration when assigning subjects to populations.

7.1. All Subjects Population

The all subjects population will include all subjects who signed the ICF and had any study assessment recorded in the database per the protocol.

7.2. Safety Population

The safety population will consist of all subjects who have received 1 dose of study drug. Subjects will be classified into hepatic function groups based on their CP score.

7.3. Pharmacokinetic Population

The PK population will consist of all subjects who have received a dose of LOXO-305, have at least 1 quantifiable plasma concentration, and for whom at least 1 PK parameter can be computed. A subject may be excluded from the PK summary statistics and statistical analysis if the subject has an AE of vomiting that occurs at or before 2 times median t_{max} . The impact of protocol deviations on PK population will be evaluated on a case-by-case basis.

8. STATISTICAL METHODOLOGY

8.1. General

Listings will be provided for all data captured in the database. Listings will include all subjects assigned to the all subjects population and include data up to the point of study completion or discontinuation. Subjects are generally considered to have completed the study if they completed all protocol-specified procedures and assessments for the EOS visit. Any subject who discontinued the study will be identified accordingly in the listings. Summaries and statistical analyses will include the subjects assigned to the relevant population based on data type.

Data analysis will be performed using the SAS[®] statistical software package Version 9.4 (or higher if upversioned during the study).

Analysis Data Model (ADaM) datasets will be prepared using Clinical Data Interchange Standards Consortium (CDISC) ADaM Version 2.1 (or higher if upversioned during the study) and CDISC ADaM Implementation Guide Version 1.2 (or higher if upversioned during the study). Pinnacle 21 Community Validator Version 3.1.0 (or higher if upversioned during the study) will be utilized to ensure compliance with CDISC standards.

Caution should be used when interpreting results from the statistical analyses conducted in this study because the sample size is not based on power calculations.

Where reference is made to 'all calculations', this includes, but is not limited to, summary statistics, statistical analyses, baseline derivation, changes from baseline, and any parameter derivations.

8.1.1. Calculation of the Summary Statistics

For continuous data the following rules will be applied:

- Missing values will not be imputed, unless specifically stated otherwise.
- Unrounded data will be used in the calculation of summary statistics.
- If the number of subjects with valid observations (n) <3, summary statistics will not be calculated, with the exception of n, minimum, and maximum.
- As ET data is not associated with any scheduled timepoint, it will be excluded from all calculations of summary statistics.
- Postdose repeats and unscheduled assessments will not be included in calculations of summary statistics.

For categorical data the following rules will be applied:

- If the categories of a parameter are ordered (eg, AE severity), all categories between the possible minimum and maximum categories will be included, even if n = 0 for a given category. If the categories are not ordered (eg, race), only those categories for which there is at least 1 subject represented will be included.
- Missing values will not be imputed, with the exception of AEs where the 'worst-case' approach will be taken (see [Section 8.6.1](#)), or unless specifically stated otherwise. A 'missing' category will be included for any parameter for which information is missing. This will ensure that the population size totals are consistent across different parameters.

All protocol deviations and data issues (eg missing data, out of protocol window) that occur during the study, including those related to COVID-19, will be considered prior to database lock for their severity/impact on how the data will be displayed.

8.1.2. Repeat and Unscheduled Readings

For vital signs measurements and ECG data only, any predose value recorded in addition to the original value or a postdose value recorded within 15 minutes of the original value will be defined as a repeat value; any postdose value recorded more than 15 minutes after the original value will be defined as an unscheduled value. For all other data types (eg, laboratory

parameters), any value recorded in addition to the original value will be defined as an unscheduled value.

The original scheduled value will be used in all calculations post dose. In the event of any repeats or unscheduled measurements taken pre-dose the values will be considered when determining the baseline value.

Post dose repeats, unscheduled assessments, and ET measurements will be excluded from all calculations, with the exception of the baseline derivation (see [Section 8.1.3](#)).

8.1.3. Definitions of Baseline and Change from Baseline

Baseline value is defined as the last non-missing measurement before administration of LOXO-305.

If the date/time of the value is incomplete or missing, it will be excluded from the baseline calculation, unless the incomplete date/time indicates the value was recorded prior to dosing.

Individual changes from baseline will be calculated by subtracting the individual subject's baseline value from the value at the timepoint. The mean change from baseline will be defined as the mean of the individual changes from baseline for all subjects.

See [Section 8.1.2](#) for more detail on handling repeat and unscheduled readings in the calculations.

8.2. Subject Disposition and Population Assignment

Subject disposition and population assignment will be listed.

A summary table by hepatic function group, CP score and NCI-ODWG separately will be provided, based on the all subjects population.

8.3. Screening Demographics and Baseline Characteristics

The screening demographics and baseline characteristics including age, sex, race, ethnicity, height, body weight, and BMI will be listed. The CP score will be listed and summarized. NCI-ODWG classification will be listed and summarized.

A summary table by hepatic function group will be provided, based on the safety population.

8.4. Prior and Concomitant Medication

Prior medication will be defined as medication that ends prior to the dose of LOXO-305. Concomitant medication will be defined as medication that starts during or after the dose of LOXO-305 or starts but does not end prior to the dose of LOXO-305.

Prior and concomitant medications will be coded using the World Health Organization Drug Dictionary (WHODrug) Global, Format B3, Version September 2020. Prior and concomitant medications will be listed.

8.5. Pharmacokinetic Assessments

8.5.1. Pharmacokinetic Analysis

The following PK parameters will be determined where possible from the plasma concentrations of LOXO-305 using noncompartmental methods in validated software program Phoenix WinNonlin (Certara, Version 8.1 or higher):

Parameter	Units ^a	Definition
AUC _{0-t}	h*ng/mL	area under the concentration-time curve from hour 0 to the last measurable concentration (t _{last}) ^b
AUC _{0-inf}	h*ng/mL	area under the concentration-time curve from time 0 extrapolated to infinity ^c
%AUC _{extrap}	%	percentage extrapolation for AUC _{0-inf}
C _{max}	ng/mL	maximum observed plasma concentration
t _{max}	h	time to maximum observed plasma concentration
λ _Z	1/h	apparent terminal elimination rate constant
t _{1/2}	h	apparent terminal elimination half-life
CL/F	L/h	apparent systemic clearance
V _{Z/F}	L	apparent volume of distribution at the terminal phase
MRT _{inf}	h	mean residence time extrapolated to infinity

^a Units are based on concentration units (provided by the bioanalytical lab or preferred units for presentation of PK parameters) and dose units used in the study. ^b Area under the concentration-time curve will be calculated using the linear trapezoidal rule for increasing and decreasing concentrations ^c Based on the last observed quantifiable concentration

The unbound fraction (f_u) in plasma, expressed as a decimal, will be calculated from protein binding concentration data as the unbound drug concentration divided by the total drug concentration in plasma. The f_u value determined for each subject will be used to calculate the following unbound LOXO-305 PK parameters for each individual subject:

C _{max,u}	Unbound C _{max} , calculated as C _{max} *f _u
AUC _{0-t,u}	Unbound AUC _{0-t} , calculated as AUC _{0-t} *f _u
AUC _{0-inf,u}	Unbound AUC _{0-inf} , calculated as AUC _{0-inf} *f _u
CL/F, _u	Unbound CL/F, calculated as Dose/AUC _{0-inf,u}
V _{Z/F,u}	Unbound V _{Z/F} , calculated as CL/F, _u /λ _Z

Additional PK parameters may be determined where appropriate.

The PK analysis will be carried out where possible using actual blood sampling times postdose. If an actual time is missing, the sample concentration result will be treated as missing unless there is scientific justification to include the result using the nominal time.

The parameters C_{max} and t_{max} will be obtained directly from the concentration-time profiles. If C_{max} occurs at more than 1 timepoint, t_{max} will be assigned to the first occurrence of C_{max} .

8.5.1.1. Criteria for the Calculation of Apparent Terminal Elimination Rate Constant and Half-life

The start of the terminal elimination phase for each subject will be defined by visual inspection and generally will be the first point at which there is no systematic deviation from the log-linear decline in concentrations.

The apparent terminal elimination rate constant (λ_z) will only be calculated when a reliable estimate can be obtained using at least 3 data points, preferably not including C_{max} , and the adjusted coefficient for determination of exponential fit (R^2 -adj) of the regression line is ≥ 0.7 . Parameters requiring λ_z for their calculation (eg, AUC_{0-inf} , $t_{1/2}$, CL/F , and V_z/F , and MRT_{inf}) will only be calculated if the R^2 -adj value of the regression line is ≥ 0.7 .

The following regression-related diagnostic PK parameters will be determined, when possible:

Parameter	Units	Definition
λ_z	1/h	apparent terminal elimination rate constant
λ_z Upper	h	end of exponential fit
λ_z Lower	h	start of exponential fit
λ_z N	NA	number of data points included in the log-linear regression
λ_z Span Ratio	NA	time period over which λ_z was determined as a ratio of $t_{1/2}$
R^2 -adj	NA	adjusted coefficient for determination of exponential fit

Where possible, the span of time used in the determination of λ_z (ie, the difference between λ_z Upper and λ_z Lower) should be ≥ 2 half-lives. If the λ_z Span Ratio is < 2 , the robustness of the $t_{1/2}$ values will be discussed in the CSR.

8.5.1.2. Criteria for Calculation and Reporting of Area Under the Concentration-time Curve

The minimum requirement for the calculation of AUC will be the inclusion of at least 3 consecutive concentrations above the lower limit of quantification. If there are only 3 consecutive concentrations, at least 1 should follow C_{max} .

AUC_{0-inf} values where the percentage extrapolation is less than 30% will be reported. AUC_{0-inf} values where the percentage extrapolation is greater than 30% will be listed but excluded from descriptive statistics and statistical analysis.

If AUC_{0-inf} cannot be determined reliably for all subjects, an alternative AUC measure, such as AUC to a fixed time point or AUC_{0-t} , may be used in the statistical analysis.

8.5.1.3. Criteria for Handling Below the Limit of Quantification or Missing Concentrations for Pharmacokinetic Analysis

Plasma concentrations below the limit of quantification (BLQ) will be assigned a value of 0 before the first measurable concentration and thereafter BLQs will be treated as missing. The following rules apply with special situations defined below:

- If an entire concentration-time profile is BLQ, it will be excluded from PK analysis.
- Where 2 or more consecutive concentrations are BLQ at the end of a profile, the profile will be deemed to have terminated and any further quantifiable concentrations will be set to missing for the calculation of the PK parameters, unless they are considered to be a true characteristic of the profile of the drug.
- If a predose plasma concentration is missing, it will be set to 0 by default within Phoenix WinNonlin.

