8.5.3. Pharmacokinetic Statistical Methodology

All PK concentrations and parameters will be listed.

Summary tables, mean (+ standard deviation [SD]) figures, overlaying individual figures, and individual figures by hepatic function group and time postdose will be provided for plasma PK concentrations using CP and NCI-ODWG classifications separately. All PK concentration figures will be produced on both linear and semi-logarithmic scales. The +SD bars will only be displayed on the linear scale.

Summary tables by hepatic function groups will be provided for all PK parameters, with the exception of diagnostic regression-related PK parameters using CP and NCI-ODWG classifications separately. Summary statistics (n, Mean, SD, CV, minimum, median, maximum, geometric mean [Geom Mean] and geometric CV [Geom CV]) will be calculated for plasma LOXO-305 PK parameters and unbound PK parameters. Excluded subjects will be listed in the PK parameter tables, but will be excluded from the statistical analysis and summary statistics and noted as such in the tables.

In addition, summary statistics for protein binding will be tabulated separately by CP and NCI-ODWG hepatic function group.

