8.5.3.1. Statistical Analysis

The primary analysis planned for this study is to evaluate the PK of LOXO-305 after a single dose in subjects with mild, moderate, or severe hepatic impairment, compared to subjects with normal hepatic function. To evaluate the effect of hepatic function group on the PK of a single dose of LOXO-305, paired t-tests will be performed for each hepatic impairment group (by CP classification) versus the normal group with respect to 1-to-1 matching on the natural log (ln)-transformed AUC_{0-t} , AUC_{0-inf} , and C_{max} . Geometric mean ratios and their corresponding 90% confidence intervals (CIs) will be calculated using the exponentiation of the mean difference and the CIs obtained for the difference in mean between each hepatic impairment group and the matching normal group.

CCI

In addition, an analysis of covariance (ANCOVA) will be performed on the ln- transformed AUC_{0-t}, AUC_{0-inf}, and C_{max}. The ANCOVA model will contain a categorical factor of population for subjects with varied-degree hepatic impairment (severe, moderate, and mild by CP classification) and healthy matched-control subjects, a categorical covariate (sex), and continuous covariates (age and BMI). Ratios of least squares means and 90% CIs will be calculated using the exponentiation of the difference between hepatic function cohort least squares means from the ANCOVA analyses on the ln-transformed AUC_{0-t}, AUC_{0-inf}, and C_{max} with the normal group as reference. In addition, an ANCOVA will be performed on the lntransformed unbound AUC_{0-t}, unbound AUC_{0-inf}, and unbound C_{max}. Similar ANCOVA analysis will be applied for evaluating the effect of hepatic function group by NCI-ODWG classification.

CCI

Additionally, a scatterplot of the ln-transformed PK parameters (AUC_{0-t}, AUC_{0-inf}, and C_{max}) and corresponding unbound PK parameters versus screening/baseline Child-Pugh total score and its individual components will be produced. The linear regression will be included on the plot, along with two-sided 90% confidence bands for the linear regression line. The Spearman rank correlation coefficient will also be calculated

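### The 30% extrapolation exclusion in SAP 8.5.1.2 names AUC0-inf only and leaves in the parameters computed from it

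*SAP*

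**What the plan says.** SAP 8.5.1.2 reports AUC0-inf when the extrapolated share is below 30%. Above that, AUC0-inf "values where the percentage extrapolation is greater than 30% will be listed but excluded from descriptive statistics and statistical analysis". No other parameter is named, and a value of exactly 30% falls under neither sentence.

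SAP 8.5.1 builds the unbound parameters from the total ones: "value determined for each subject will be used to calculate the following unbound LOXO-305 PK parameters for each individual subject". AUC0-inf,u is AUC0-inf times fu. The clearance entry reads "Unbound CL/F, calculated as Dose/AUC", the AUC meant being AUC0-inf,u, and Vz/F,u is that clearance divided by lambda-z.

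SAP 8.5.1.1 has a separate quality rule, an adjusted R-squared of at least 0.7. That rule is carried forward to "Parameters requiring λ_z for their calculation", with AUC0-inf, t1/2, CL/F, Vz/F and MRTinf as examples.

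SAP 8.5.3 calls for summary statistics on plasma LOXO-305 "PK parameters and unbound PK parameters". SAP 8.5.3.1 models total AUC0-t, AUC0-inf and Cmax, then adds: "In addition, an ANCOVA will be performed on the lntransformed unbound" versions of the same three. SAP 3.1 lists all of these parameters as primary endpoints, apart from the regression diagnostics. The protocol has no extrapolation rule, so the SAP is the only control.

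**The concern.** The 30% rule exists because the SAP regards an AUC0-inf that is largely extrapolated as too unreliable to summarise or model. Multiplying that value by fu, or dividing the dose by it, does not make it more reliable. The rule as worded removes the value under one name and admits it under several others.

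Two things are at stake. The total and unbound AUC0-inf ratios could rest on different subjects, so they could differ for a reason unrelated to the drug. And the summarised CL/F, Vz/F and MRTinf could cover a subject whose AUC0-inf is missing from the adjacent rows, so that average clearance no longer corresponds to average exposure.

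**Working it through.** The plan states no figure to reproduce on this point. The check has three parts.

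**1. Is the extrapolated share the same for total and unbound?** From protocol 8.4, AUC0-inf = AUC0-t + Ct/λz. One fu applies per subject, so

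(fu × Ct/λz) / (fu × AUC0-inf) = (Ct/λz) / AUC0-inf.

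A subject at 31% for total is at 31% for unbound. CL/F and Vz/F rest on the same extrapolated area. MRTinf depends on it more heavily: under mono-exponential decline, when 30% of AUC is extrapolated, 0.3 × (1 + ln(1/0.3)) = 0.3 × 2.204 = 66% of the area under the first-moment curve is extrapolated.

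**2. When does the rule fire?** Inputs: last sample 168 h (protocol 3.1); half-life about 20 h (protocol 1.4.2, in patients, from 0–8 h sampling with an imputed 24 h value). Assuming mono-exponential decline, extrapolated share = 2^(−t_last / t½).

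- Half-life 20 h, full sampling: 168/20 = 8.4 half-lives, share 0.3%.
- Assumed longer half-lives, full sampling: 40 h gives 5%, 60 h 14%, 80 h 23%, 100 h 31%.
- Half-life at which the share reaches 30% at 168 h: 168 × ln 2 / ln(1/0.3) = 96.7 h, and 96.7/20 = 4.8. A one-compartment oral model (absorption rate constant assumed 1.8/h) gives 30.1% at 96.7 h.
- Truncated profile: the share exceeds 30% if the last sample falls before t½ × 1.737, which is about 35 h at a 20 h half-life and 69 h at 40 h.

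**3. How far apart can the two ratios move?** Take n subjects in a group, fu constant, and one subject with k times the AUC0-inf of the rest. If that subject is dropped from the total ratio but kept in the unbound one, the unbound ratio is larger by the factor k^(1/n).

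Illustration with n = 6, the completion target per Child-Pugh group: five subjects at 2 times control and one at 5 times control, so k = 2.5.

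- Total ratio, 5 subjects: 2.00.
- Unbound ratio, 6 subjects: exp[(5 ln 2 + ln 5)/6] = 2.33.
- Gap: 2.33/2.00 = 2.5^(1/6) = 1.165, about 17%, with no change in binding.
- Geometric mean CL/F relative to control: 1/2.33 = 0.43 with the subject kept, against 1/2.00 = 0.50 implied by the reported AUC0-inf.

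The example is internally consistent. If only clearance changes, 5 times the AUC from a 20 h half-life means 100 h and 31% extrapolation, while the 2-fold subjects are at 40 h and 5%.

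| k | n = 4 (NCI-ODWG aim) | n = 6 | n = 8 |
|---|---|---|---|
| 1 | 1.00 | 1.00 | 1.00 |
| 1.5 | 1.11 | 1.07 | 1.05 |
| 2 | 1.19 | 1.12 | 1.09 |
| 2.5 | 1.26 | 1.17 | 1.12 |
| 3 | 1.32 | 1.20 | 1.15 |

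The row k = 1 is the truncated profile with a typical AUC: no shift. These are unadjusted geometric means; least squares means from the ANCOVA would differ somewhat.

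**The case against.** The best counter-argument is that the wording need not be read so narrowly. The examples in SAP 8.5.1.1 are introduced as examples and omit the unbound forms too, so silence in 8.5.1.2 does not prove that those forms were meant to stay in. A programmer could take AUC0-inf to include unbound AUC0-inf. The TFL shells are not available, and parts of SAP 8.5.3.1 are redacted. This stands: the literal reading is one reading, not a certain outcome. It is still a reason to specify, and the other provisions do not settle the matter. The line "Excluded subjects will be listed in the PK parameter tables, but will be excluded from the statistical analysis and summary statistics" works at subject level and is not tied to the 30% rule. The rule on not-reported and not-calculated values (SAP 8.5.2) does not cover values that were calculated. The alternative AUC in 8.5.1.2 is optional and does not mention derived parameters.

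The trigger is also remote, and an affected subject would be visible. Above 30% extrapolation the last sample lies within 1.74 half-lives, so the λz span ratio is below 2 and SAP 8.5.1.1 requires the half-life to be discussed in the report. The extrapolated share is listed and each summary shows n. This limits the harm but does not remove the value from the model.

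A reader might infer that the trial identifies a binding effect by comparing the total and unbound AUC0-inf ratios, so that the gap above would become a false binding finding. The documents do not support that. No such comparison is planned. Protein binding is summarised directly by group (SAP 8.5.3), and total and unbound AUC0-t and Cmax, which the 30% rule does not touch, are analysed alongside. Nor does the problem extend to ratios for CL/F, Vz/F or MRTinf: these are only described, and MRTinf has no unbound form.

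**Conclusion.** The point holds as a rule with too narrow a scope. SAP 8.5.1.2 excludes an unreliable AUC0-inf but, read literally, keeps it in the ANCOVA of unbound AUC0-inf and in five descriptive summaries (CL/F, Vz/F, MRTinf, CL/F,u, Vz/F,u). The ratio mismatch is confined to AUC0-inf against AUC0-inf,u.

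Practical impact is probably low. With full sampling the rule needs a half-life near 97 h. The 20 h reference is weak and comes from patients, not from subjects selected for hepatic impairment, so longer values are possible. If one subject is affected in a group of 6, the gap runs from none (typical AUC) to about 17% (2.5 times the others). The size rests on constant fu, mono-exponential decline, the assumed k and unadjusted geometric means.

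**What to change.** Before database lock, reword SAP 8.5.1.2 along these lines: *Where %AUCextrap is 30% or greater, AUC0-inf and every parameter derived from it (AUC0-inf,u, CL/F, CL/F,u, Vz/F, Vz/F,u, MRTinf) are shown in listings only and do not enter summary statistics or statistical models.* This puts the total and unbound AUC0-inf analyses on the same subjects wherever fu is available (both ratios are 2.00 in the illustration), and it assigns the case of exactly 30%.

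The cost is one sentence and a slightly smaller n for those parameters when the rule fires. A sensitivity ANCOVA that keeps all calculable AUC0-inf values is optional. The exclusion does remove long-half-life subjects, but total and unbound AUC0-t are already analysed without it.
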